In a prospective observational feasibility study,⁷ our group evaluated 38 patients with psychiatric emergencies who presented to the ED between April and June 2020. Patients were interviewed by two psychiatrists, one face-to-face, and one via video-link, in varying chronological order. Interviewers and a senior psychiatry resident who observed both interviews determined the diagnosis, recommended disposition, and decided whether involuntary admission was warranted for this patient. Patients and psychiatrists completed acceptability post-assessment surveys.

We compared three pairs of assessments for agreement using Cohen's kappa: between the face-to-face interviewer and the remote interviewer, between the observer and the face-to-face interviewer, and between the observer and the remote interviewer. Agreement between raters on recommended disposition and indication for involuntary admission as measured by kappa was "strong" to "almost perfect", ranging from 0.81 to as high as 0.95 (Figure 1). Partial agreement between the raters on diagnosis was "strong", ranging from 0.81 to 0.85. Psychiatrists' and patients' satisfaction rates, and psychiatrists' perceived certainty rates, were comparably high in both face-to-face and telepsychiatry groups. It is notable that while agreement between psychiatrists was not perfect, especially on precise diagnosis, agreement was not materially affected by interviewing the patient remotely. It is also notable that **agreement on recommended disposition and the need for involuntary admission was especially high**. We

Protocol Name: Telepsychiatry Emergency; Version: 1.0; Date Nov 5, 2021
concluded that telepsychiatry is a reliable and acceptable alternative to face-to-face psychiatric assessments in the ED setting.

[figure not shown]

Figure 1: Agreement between raters on recommended disposition, indication for involuntary admission and diagnosis (n=38).

In addition to these measures of agreement, we also measured patients' and providers' satisfaction with the process, as well as providers' level of confidence in their decisions. Patients and providers reported similar levels of satisfaction with remote vs. in-person interviews. Providers reported a similar level of confidence in their clinical decisions with remote vs. in-person interviews.

c. Conceptual Framework and Ethical Analysis

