The arguments in favor of virtual triage in the ED are much stronger. We expect that this change will reduce risk to patients, and risk to others, from violent outbursts. We expect that both phases will reduce patient discomfort, distress, and fear. Lessening decompensation by patients in the ED will allow therapeutic strategies to commence earlier, contributing to earlier recovery and earlier hospital discharge.

It is worth noting that our project is defensible on the basis of benefit to patients alone (otherwise, we would not consider it). There are other likely benefits, which do not enter directly into our calculus. This project is likely to reduce ED crowding. Also, this project will save the attending psychiatrist the need to travel to the hospital for most evaluations. We emphatically repeat that while these are indeed benefits, they are not the basis for us performing the study, nor would they be a sufficient reason for this change in policy.

2. Objectives

- i. We will implement tele-psychiatry evaluations in the ED.
- ii. We will evaluate the impact of this strategy on patient outcomes and healthcare utilization, compared to historical controls.

3. Working Hypotheses

- a. Remote video psychiatric examination is safe and effective, as measured by clinical outcomes, when compared to usual practice. Patients will spend fewer minutes in the ED, compared with historical controls. There will be fewer violent incidents in the ED. There will not be an increase in the frequency of reversal of involuntary hospitalization, which would imply that a patient was needlessly admitted.
- b. Implementation of telepsychiatry will be feasible within the current context, infrastructure, and resources.

4. Comprehensive description of study design and methodology:

Patient Population

We will recruit study participants from the Jerusalem Mental Health Center, located at Kfar Shaul and Ichilov Medical Center. We will obtain a waiver of informed consent, as this will be a change in standard procedure for all patients for the duration of the study.

We will include all patients who require an ED interview and an involuntary admission decision by a senior psychiatrist. We will compare patients from the three months prior to the study (approximately 60, based on usual rates of admissions) with patients from the three months of the study (also 60).

The absence of exclusion criteria will ensure that the study results will be broadly generalizable.

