Independent Variables (The Intervention)

In each study phase, the independent variable will be the study intervention, which will be organized by time. Patients in the pre-intervention period (3 months) will be managed under usual care, and will be the comparison group. Patients in the post-intervention period (3 months) will be managed using the study intervention, and will be the “intervention” group.

Usual care is that patients with psychiatric emergencies are evaluated face-to-face in the ED by a senior psychiatrist for possible involuntary admission. The intervention is that this evaluation will take place via video-link.

Dependent Variables

Dependent Variables

Variable	Type	Data Collection Method
Interobserver Variability	Binary	All video interviews will be recorded. A second senior psychiatrist, blinded to the admission decision, will determine whether admission was warranted based on the recording.
Reversal of Admission	Binary	An involuntary admission which is reversed within 24 hours implies an unnecessary admission. The proportion of admissions reversed within 24 hours will be measured.
Emergency Room Length of Stay	Continuous (minutes)	Measured from the time of arrival in the ED until the patient physically leaves the ED – to go home or to go to the psychiatry ward. Already collected as part of routine practice.
Time from ED arrival to assessment	Continuous (minutes)	We will measure this ourselves, starting with the pre-intervention period. We will measure time until the senior psychiatrist begins his/her face-to-face or virtual assessment.
Violent Incidents in the ED	Binary (any/none)	As recorded by ED staff and adjudicated by blinded review of the chart by a senior psychiatrist.
Patient satisfaction with ED course	Ordinal	We will ask patients to rate their overall satisfaction with their stay in the ED, from 1-5 (very dissatisfied – very satisfied), as they are leaving – starting with the pre-intervention period.
Staff satisfaction with ED flow	Ordinal	We will ask physicians, nurses, and other staff to rate their overall assessment of ED flow, from 1-5, at the end of each month
Duration of hospitalization	Continuous	From the time of entering the ward until the time of leaving the hospital, in hours

Statistical Analyses

We will be comparing the pre-intervention period with the post-intervention period. Above, we have outlined the dependent variables for each phase, and how we will collect them.

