We will start by comparing the pre- and post-groups on important baseline characteristics. These will include age, sex, ethnic/social group (Haredi, Arab, General Population), socioeconomic status, and underlying condition (schizophrenia, bipolar disorder, other). We will compare these variables between pre- and post-groups using appropriate bivariate tests (t-test, chi-square). If we find a statistically significant imbalance ($p < 0.05$), we will utilize a multivariable analysis in the main analysis to correct for the imbalanced factors. We do not propose to control for all potential covariates because of limited sample size.

In the main analysis, we will compare the dependent variables explained above between the pre- and post-periods. For continuous variables, we will use an unpaired t-test. For categorical variables, we will use a chi-square test. We will perform two-tailed tests, and will consider $p < 0.05$ to be statistically significant. In the event that we have detected an important between-group imbalance, we will use an appropriate regression model (logistic or generalized linear model), controlling for only the factors that have been found to be unbalanced.

Potential Sources of Bias

A sample size of 60 each in the pre- and post-intervention groups will make it unlikely, but not impossible, that random chance will lead to important between-group imbalance on measured factors. We will assess for such imbalance as part of the analysis plan, as noted above. If there are important differences, we will conduct multivariable analyses to control for a limited number of important unbalanced covariates.

Justification of Sample Size and Study Duration

The study duration is dictated by the maximal duration of a study funded by Machon HaLeumi. The sample size is dictated by the approximate number of patients admitted to our center each month. With 60 patients in the pre-intervention period and 60 in the post-intervention period, we will have statistical power to show a large effect size for some variables, and a moderate effect size for others. For example, if we assume that the average time in the ED is currently

3 ± 1 hours, and that the Phase 1 intervention will reduce this time by one hour, with 60 patients in each group, we would have 80% power to detect such a difference.

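### Interobserver variability is taken only from recorded video interviews, so its planned pre-versus-post comparison has no pre-period data and needs a one-group analysis instead (minor correction)

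*Combined protocol and SAP*

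**What the plan says.** The Dependent Variables table in Section 4 has eight rows. The first, Interobserver Variability, is typed as binary, and its only data source is this: "All video interviews will be recorded. A second senior psychiatrist, blinded to the admission decision, will determine whether admission was warranted". The rating is made from the recording.

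The section on the intervention describes the comparison group's care: "Usual care is that patients with psychiatric emergencies are evaluated face-to-face in the ED by a senior psychiatrist". Video assessment belongs to the post-intervention period only.

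Statistical Analyses then opens with "Above, we have outlined the dependent variables for each phase, and how we will collect them" and goes on: "In the main analysis, we will compare the dependent variables explained above between the pre- and post-periods". Continuous variables get an unpaired t-test. For the rest, "For categorical variables, we will use a chi-square test". No variable is exempted, and no agreement statistic is named for this study. Kappa appears only in Section 1b, on the earlier 38-patient study ("Agreement between raters on recommended disposition and indication for involuntary admission as measured by kappa was").

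Two further rows, patient and staff satisfaction, are typed as ordinal. The analysis text names tests for continuous and categorical variables only.

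**The concern.** A planned test needs data from both periods. For this outcome the data source exists in one period only, so the analysis as written cannot be run.

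This is also the only listed outcome in which a blinded second psychiatrist checks the admission decision. Reversal within 24 hours is counted among admissions, so it can flag only a needless admission. The second reading could also flag a patient who was not admitted but whom the reviewer would have admitted. If its analysis is settled only once the data are in, the analyst must choose between raw agreement and kappa, and must decide what to do with interviews that ended undecided. Those choices can change how the same data read.

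The ordinal gap is smaller. If the 1-5 patient rating is treated as categorical, the chi-square test ignores the order of the categories and loses power.

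**Working it through.** The documents give no figure for this outcome, so there is none to reproduce. The main check is structural.

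**1. Which period supplies data.** The second rating needs a recording, recordings are of video interviews, and video interviews occur only after the change. Ratable interviews are therefore 0 of about 60 in the pre-period and at most 60 in the post-period. In a 2x2 chi-square, each expected count is row total × column total / n. With a pre-period row total of 0, both expected counts in that row are 0 and the statistic is undefined. A trial table with rows (0, 0) and (54, 6) fails for this reason. This affects 1 of 8 planned comparisons.

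**2. What a one-group analysis can show.** The inputs here are assumptions: 60 interviews with a decision, 55 agreements, and four shares admitted by the video psychiatrist. The documents do not give the share admitted.

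Raw agreement is p = 55/60 = 0.917. The Wilson 95% interval is [p + z²/2n ± z√(p(1−p)/n + z²/4n²)] / (1 + z²/n). With z = 1.96 and n = 60 this is (0.9487 ± 0.0769)/1.0640, or 0.819 to 0.964.

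Kappa = (p − pe)/(1 − pe), where pe = ab + (1−a)(1−b), and a and b are the shares admitted by the video psychiatrist and the reviewer.

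| Both admit / video only / reviewer only / neither | a | b | pe | kappa | percentile-bootstrap 95% CI |
|---|---|---|---|---|---|
| 28/2/3/27 | 0.50 | 0.517 | 0.500 | 0.83 | 0.67 to 0.97 |
| 39/3/2/16 | 0.70 | 0.683 | 0.573 | 0.80 | 0.62 to 0.96 |
| 45/3/2/10 | 0.80 | 0.783 | 0.670 | 0.75 | 0.50 to 0.94 |
| 51/3/2/4 | 0.90 | 0.883 | 0.807 | 0.57 | 0.14 to 0.88 |

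For the last row, (0.9167 − 0.8067)/(1 − 0.8067) = 0.1100/0.1933 = 0.569. The bootstrap used 50,000 multinomial resamples. Raw agreement is identical in all four rows; only the share admitted moves kappa.

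**3. The ordinal patient rating.** Simulation with 60 per group, two-sided 5%, 10,000 runs, a proportional-odds shift with an assumed odds ratio of 2.5, and three assumed pre-period distributions over scores 1 to 5:

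| Pre-period distribution (%) | chi-square | Wilcoxon | t-test |
|---|---|---|---|
| 15/20/30/20/15 | 0.585 | 0.799 | 0.798 |
| 30/30/20/15/5 | 0.576 | 0.798 | 0.796 |
| 5/10/20/35/30 | 0.553 | 0.779 | 0.744 |

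Allowing for simulation error, power is about 55-60% for chi-square and 77-81% for Wilcoxon. With no effect, all three tests reject in 0.045 to 0.052 of runs, so chi-square is valid but less efficient.

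**The case against.** The strongest reply is that this is an omission of wording that cannot yield a wrong result. With no pre-period row, any analyst must stop and describe the video period alone, which is what the table row already suggests. That stands as a reason to call the point minor. It does not remove it: the text sends every listed variable to the pre/post test, and the mention of variables for each phase is no exemption, because each phase has its own pre and post periods.

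Some stronger readings are tempting, and the documents do not support them.

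- A reader might infer that the safety case or the main analysis fails. The hypotheses in Section 3 rest on ED time, violent incidents and reversal ("There will not be an increase in the frequency of reversal of involuntary hospitalization"), not on interobserver agreement.
- A reader might treat the earlier study's kappas of 0.81 to 0.95 as a benchmark. No agreement target is set for this study. The earlier range covers two kinds of rating and three rater pairs, with two separate interviews and a live observer; here one reviewer watches a recording of the same interview.
- A reader might infer that in-person fallback cases will distort the result. Section 1c calls them rare, and the documents give no count.
- A reader might infer that staff ratings are missing from the pre-period. The staff row is silent on this, but only two of the eight rows state a pre-period start, so silence shows little.

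On the patient rating, it is fair to say that a 1-5 score can be read as categorical, which would make chi-square the assigned test. Preferring a rank-based test is then a matter of efficiency, not validity.

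**Conclusion.** The concern holds in a limited form. One of eight planned comparisons cannot be computed as written, because its data source exists only in the intervention period. This follows from the text alone and rests on no assumed figure. The correction is minor.

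The kappa range of 0.83 to 0.57 shows why the replacement analysis should be fixed in advance and reported with its table. It is illustrative and rests on the assumed 55 of 60 agreements and the assumed shares admitted. The loss of power for patient satisfaction arises only if chi-square is the test used, and its size depends on the assumed odds ratio and base distributions.

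**What to change.** - Take Interobserver Variability out of the pre/post comparison.
- For the intervention period only, report percent agreement (Wilson 95% CI) and Cohen's kappa (bootstrap 95% CI) between the video psychiatrist's admission decision and the blinded reviewer, with the full 2x2 table so that the share admitted is visible.
- Count and report separately any video interviews that ended without an admit or not-admit decision and went to in-person evaluation. An undecided view has no cell in the table and should not be forced into one.
- State that the study gives no face-to-face comparator for agreement and that no agreement target is set.
- Name a Wilcoxon rank-sum test or a proportional-odds model for the 1-5 patient satisfaction rating.

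The cost is a few lines of analysis text and a count of undecided interviews; no new reader or procedure is needed. The downside is that the kappa interval is wide at 60 interviews, and very wide if most patients are admitted.

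Rating pre-period interviews as well would restore a comparison, but it would add a procedure the plan does not describe. At 60 per group it would have only about 45% power for an assumed 95% versus 85% agreement.

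### Six or seven pre/post outcomes per phase are each tested at two-sided 0.05 with no primary outcome, success rule or multiplicity control, so the lead result can be chosen after the data are seen

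*Combined protocol and SAP*

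**What the plan says.** The Dependent Variables table in section 4 lists eight outcomes, unranked: interobserver variability, reversal of admission, ED length of stay, time from arrival to assessment, violent incidents, patient satisfaction, staff satisfaction and duration of hospitalization. Under Statistical Analyses the list is applied to every phase ("Above, we have outlined the dependent variables for each phase, and how we will collect them") and then carried whole into the principal comparison: "In the main analysis, we will compare the dependent variables explained above between the pre- and post-periods". The tests are set by variable type ("For continuous variables, we will use an unpaired t-test. For categorical variables, we will use a chi-square test"), and one threshold covers them all: "We will perform two-tailed tests, and will consider $p < 0.05$ to be statistically significant".

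The conclusion to be supported is in section 3: "Remote video psychiatric examination is safe and effective, as measured by clinical outcomes, when compared to usual practice". Three expectations follow it: less time in the ED, fewer violent incidents and no rise in reversed admissions.

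The only power figure is for ED time, in the sample-size justification of section 4. It is offered as an example ("if we assume that the average time in the ED is currently" 3 ± 1 hours, reduced by one hour). The sample size itself is attributed to the number of patients admitted, not to that calculation.

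**The concern.** The plan has a threshold for each test but no rule for turning six or seven test results into one conclusion. Nor does the emphasis in the text settle which outcome leads:

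- The abstract (Methods of Data Collection) names ED time, violent incidents and duration of hospitalization.
- Section 3 names ED time, violent incidents and reversal of admission.
- The sample-size justification uses ED time, as an illustration.
- Section 5 expects faster placement, but says the benefit will show up in violent incidents and hospital stay.

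An analyst could follow the plan to the letter and still decide afterwards which of these is the finding. The chance that something reaches significance when nothing has changed is then well above 5%. This matters because the abstract and section 5 foresee a positive result entering official policy on involuntary admission, and because the comparison is with historical controls, where choosing the outcome afterwards adds avoidable uncertainty.

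**Working it through.** **The plan's own figure.** The documents state no overall error rate. Their one calculated figure is 80% power for a 1 h reduction, SD 1 h, 60 per group. The standardized shift is 1/(1 × √(2/60)) = 5.48, and power is Φ(5.48 − 1.96) = Φ(3.52) ≈ 99.98% (99.97% with the noncentral t). The 80% does not reproduce. That is a separate point, used here only to show what the fix costs.

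**How many tests.** Interobserver variability has no pre-period value. It is rated from video ("All video interviews will be recorded. A second senior psychiatrist, blinded to the admission decision, will determine whether admission was warranted based on the recording"), and usual care is face-to-face. Seven outcomes remain. Staff satisfaction is uncertain: its row ("We will ask physicians, nurses, and other staff to rate their overall assessment of ED flow, from 1-5, at the end of each month") does not say that collection begins before implementation, whereas the rows for time to assessment and patient satisfaction do. So there are six or seven tests. No test is named specifically for the two ordinal outcomes; I assume each is tested at 0.05.

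**Independent tests, difference in either direction:** 1 − 0.95^k.

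| Outcomes counted | k | Chance of at least one false positive |
|---|---|---|
| Named in section 3 | 3 | 14.3% |
| Named across the abstract and sections 3 and 5 (ED time, violence, reversal, hospital stay) | 4 | 18.5% |
| Without staff satisfaction | 6 | 26.5% |
| With staff satisfaction | 7 | 30.2% |

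**Favourable direction only:** 1 − 0.975^k, since half of each two-sided 0.05 lies on the favourable side. For k = 7 this is 16.2%, for k = 6 it is 14.1% and for k = 3 it is 7.3%. The comparator for a single test is 2.5%.

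**Correlation.** The documents give none, and independence cannot hold exactly because ED length of stay contains the time to assessment. Simulating seven equally correlated normal statistics (400,000 draws) gives:

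| Assumed correlation | Either direction | Favourable only |
|---|---|---|
| 0 | 30% | 16% |
| 0.3 | 27% | 14% |
| 0.5 | 23% | 11.5% |
| 0.7 | 18% | 9% |

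These figures take each test to have a true size of 5%. For a rare binary outcome the chi-square test at 60 per group falls below that (1.9% at an assumed event rate of 2%, 4.6% at 5%), so 30% is an upper value.

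**The case against.** A reader might infer that the plan lets any one of seven significant results establish safety and effectiveness, with a 30% risk of a false claim. The documents do not support that, for four reasons.

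- The plan sets a threshold for calling a single comparison significant. It nowhere says that one such result is enough. What is missing is the success rule.
- Section 3 ties the claim to clinical outcomes and names three. Staff satisfaction with ED flow would not naturally carry it. If all three expectations had to hold together, testing several outcomes would not inflate the error of the joint claim. The plan neither states nor excludes that reading.
- The 30% assumes independence and counts differences in either direction, including harm. A false claim of benefit needs a favourable result, about 16% at most.
- The safety part is an expectation of no increase. The risk there is that a non-significant test with no margin is read as reassurance, and a family-wise error rate for differences does not measure that risk.

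A reader might also double the count to 14 tests over two phases and quote 51% (1 − 0.95^14). That is an upper bound. The abstract compares each stage with the three months before the study, so the phases may share controls and their tests may be correlated.

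It can fairly be added that section 4 calls this a small feasibility study that may not be definitive for some outcomes. The same section also declares a Type 1 hybrid design, whose main emphasis is effectiveness, and the policy aim is explicit. This tempers the point without removing it. All four corrections above stand, but the absence of a primary outcome, a testing order, a multiplicity rule and a success rule is not answered anywhere in the documents.

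**Conclusion.** The point holds as a gap in the decision structure: six or seven comparisons per phase share one unadjusted threshold, nothing says which of them decides the study, and different sections stress different outcomes. The chance of at least one false-positive difference per phase is up to about 30% for seven independent tests and 26.5% for six, and roughly 18% to 27% for seven at assumed correlations of 0.7 down to 0.3. Counting only favourable results it is about 16% for seven independent tests. Confined to the three outcomes of section 3 it is 14.3% two-sided, or 7.3% favourable. Even the smallest of these is nearly three times the corresponding single-test rate (7.3% against 2.5%). The change should be made before the data are analysed; it does not call the data collection into question.

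**What to change.** In section 4, Statistical Analyses:

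1. Name ED length of stay as the single primary effectiveness outcome, tested at two-sided 0.05. It is the first-named effectiveness hypothesis in section 3, is already collected routinely, and is the only outcome with a power illustration. It should not be described as the basis of the sample size, which the plan attributes to patient numbers.
2. Make the remaining pre/post outcomes secondary. Either apply a Holm adjustment across them, or report estimates with 95% intervals and make no significance claim. If Holm is chosen and overall control is wanted, test the secondary outcomes only after the primary is significant.
3. Report reversal of admission as a safety outcome by the confidence interval for the difference between periods, and do not treat a non-significant test as evidence of no increase.
4. State whether staff satisfaction is collected in the pre-period, so that the number of comparisons is fixed.

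The cost is protocol wording, with no extra patients or data. The downside is that secondary outcomes can no longer carry the effectiveness conclusion alone. Power for the primary is not a constraint under the plan's own inputs (SD 1 h, 1 h reduction, 60 per group): it is above 99%, and 99.7% even at a Bonferroni level of 0.05/7 = 0.0071. The 80% stated for the same inputs should be corrected separately.

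### No test is named for the ordinal outcomes; on the natural reading, patient satisfaction (1-5) gets a chi-square test that ignores the order of the ratings

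*Combined protocol and SAP*

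**What the plan says.** The Dependent Variables table in section 4 sorts eight outcomes into three types: binary, continuous and ordinal. Two are ordinal. For patients: "We will ask patients to rate their overall satisfaction with their stay in the ED, from 1-5", anchored from very dissatisfied to very satisfied and asked as they leave. For staff, physicians, nurses and others are to "rate their overall assessment of ED flow, from 1-5, at the end of each month".

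The Statistical Analyses section then gives rules for two types: "For continuous variables, we will use an unpaired t-test. For categorical variables, we will use a chi-square test". The abstract gives the same pair. If a baseline imbalance is detected, "we will use an appropriate regression model (logistic or generalized linear model"), controlling only for the unbalanced factors. On significance: "We will perform two-tailed tests, and will consider $p < 0.05$ to be statistically significant".

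No rank test, trend test or ordinal model is named anywhere. The documents give no expected distribution of ratings, effect size, response rate or power for either satisfaction outcome.

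**The concern.** The table separates ordinal from continuous, so the t-test rule does not obviously reach a five-level rating, and the rule for categorical variables is the one left. A Pearson chi-square on a 2 x 5 table treats the five levels as unordered labels. Shuffle the columns and the statistic is unchanged. A significant result therefore says that the pattern of ratings differs between periods, not that ratings rose. It also spreads a simple upward shift over four contrasts, so a real improvement is more often missed.

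Patient satisfaction is the only outcome in the table that patients report themselves, and the conceptual framework lists less patient discomfort among the arguments for the intervention. The sample size is set by admission numbers and the funding period, so lost power cannot be bought back by enrolling more patients. The choice of test is the available lever.

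**Working it through.** **The plan's own figure.** The plan has no power figure for satisfaction. Its only worked example concerns ED time: "3 ± 1 hours, and that the Phase 1 intervention will reduce this time by one hour", with 60 per group and a stated power of 80%. Those inputs give a standardised difference of 1/1 = 1 and power Φ(1 × √(60/2) − 1.96) = Φ(5.48 − 1.96) ≈ 99.98%, so the 80% does not reproduce. That is a separate matter and has no bearing on satisfaction.

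**Inputs from the plan.** Five ordered levels (Dependent Variables table); two-sided 0.05 (Statistical Analyses); 60 per period ("With 60 patients in the pre-intervention period and 60 in the post-intervention period", sample size section).

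**Inputs assumed.** Everyone responds. Six baseline distributions over levels 1 to 5:
- uniform: .20 each
- symmetric: .10, .20, .40, .20, .10
- low-skewed: .30, .30, .20, .15, .05
- high-skewed: .05, .10, .20, .35, .30
- U-shaped: .30, .15, .10, .15, .30
- strong ceiling: .03, .05, .12, .30, .50

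The post-period distribution is a proportional-odds shift: the odds of rating at or below each level are divided by the odds ratio (OR). For example, from the uniform baseline with OR 2.5, P(level 1) has odds .2/.8 = .25, then .25/2.5 = .10, so .10/1.10 = .091. The full set becomes .091, .120, .164, .240, .385.

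**Analytic check.** The chi-square has (2 − 1)(5 − 1) = 4 degrees of freedom. An ordered test on 1 degree of freedom with 80% power has noncentrality (1.960 + 0.842)² = 7.85. Put that noncentrality on 4 degrees of freedom (5% critical value 9.49 instead of 3.84) and power is 59.5%, a loss of 20.5 points. Where the ordered test has 40% to 90% power, the loss is 16 to 22 points.

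**Simulation.** 20,000 replicates per cell and 60 per period. The tests are the Pearson chi-square, Wilcoxon-Mann-Whitney with tie correction, and the t-test on the scores. Entries are percentages, with the range over the six baselines.

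| OR | Chi-square | Wilcoxon | t-test | Wilcoxon minus chi-square (points) |
|---|---|---|---|---|
| 1 | 4.1-4.7 | 4.9-5.1 | 4.8-5.2 | type I error |
| 1.5 | 11.1-14.2 | 20.7-23.4 | 18.6-23.7 | 9.0-10.5 |
| 2 | 27.6-35.1 | 48.3-56.7 | 42.9-56.6 | 20.4-22.0 |
| 2.5 | 46.4-59.0 | 70.1-80.1 | 63.8-79.9 | 21.0-23.7 |
| 3 | 62.5-75.8 | 83.8-91.6 | 78.1-91.2 | 15.6-21.3 |
| 4 | 82.5-93.4 | 94.8-98.8 | 91.3-98.8 | 5.4-12.3 |

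For OR 2 to 3 the gap is 15.6 to 23.7 points. A repeat run on four assumed baselines gave about 15 to 24, the range quoted here.

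**t-test against Wilcoxon.** The t-test loses less than 1 point on four of the six baselines. It loses at most 77.0 − 73.6 = 3.4 points on the high-skewed baseline and 70.1 − 63.8 = 6.3 points on the ceiling baseline (both at OR 2.5).

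**Fewer respondents.** For OR 2 to 3 on the uniform, symmetric and low-skewed baselines, the chi-square loses about 18 to 23 points at 45 per period and about 14 to 25 at 30 per period.

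**The case against.** A reader might infer that the plan has chosen the chi-square for satisfaction and has thereby given up a fixed 15 to 24 points of power. The documents do not support that.

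- The plan never assigns the chi-square to ordinal outcomes. It is the natural reading of the two rules, but a t-test on 1-5 scores is common practice and is one of the two tests named. It would give a direction and lose almost nothing. This stands: depending on a choice left open, the cost runs from about 0 to about 24 points.
- The loss depends on the shape of the change. It needs a roughly proportional-odds shift and is largest at moderate odds ratios. In an assumed polarising change, from the symmetric baseline to .25, .15, .20, .15, .25, the chi-square has 84% power and Wilcoxon 6%. This stands as a limit on the figure. It does not defend the chi-square here, because polarisation is not the improvement that the protocol argues for.
- The plan does name a regression model, and a proportional-odds model is a form of logistic regression. So an ordinal adjusted analysis is not excluded. It is not specified either, and it applies only after a baseline imbalance.
- The 2 x 5 table of proportions would show which way ratings moved. True, but the p-value would not test that movement.
- Satisfaction appears in no working hypothesis. Those name ED time, violent incidents and reversal of admission, and the Significance section adds shorter stays. The protocol also accepts that some outcomes will not be settled. This stands and sets the severity.

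**Conclusion.** The concern holds in a limited form. The firm defect is that two outcomes are typed as ordinal and no test is named for that type. On the natural reading, patient satisfaction goes to a 4-df chi-square, a poor match for the question of whether patients were more satisfied. Given 60 respondents per period and a proportional-odds shift, the cost against Wilcoxon-Mann-Whitney is about 15 to 24 points of power for OR 2 to 3 and about 5 to 12 at OR 1.5 or 4. These shifts and baselines are assumptions, since the documents supply none. If a t-test on the scores was meant, the cost is about 0 to 1 point in most cases and up to about 6 with a strong ceiling; what remains is an unstated choice that could be made after the data are seen. Type I error is near or slightly below 5% for all three tests. Staff satisfaction has the same gap, and monthly ratings from the same staff would not be independent. Severity is minor: none of the working hypotheses turns on this test.

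**What to change.** Add to the Statistical Analyses section:

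> Patient satisfaction (1-5) will be compared between periods with the Wilcoxon-Mann-Whitney test, not the chi-square test, and reported as the common odds ratio from a proportional-odds model with 95% CI. If adjustment is needed, the unbalanced factors are added to that model.

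Add a further sentence for staff satisfaction: a method that uses the order of the ratings, allowing for repeat monthly ratings by the same staff member where these can be linked.

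The patient sentence needs no new data and does not change how the study is run. The staff sentence needs only a decision on whether monthly ratings can be linked to an anonymous staff code.
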